6. GENERAL ANALYSIS DEFINITIONS

6.1 TREATMENTS

In the Phase I part, treatments are not randomized (open-label, dose escalation). Different dose levels (planned and intermediate) of the investigational medicinal product will be evaluated. The data will be presented for all dose cohorts separately, in particular, patients will be analysed by the treatment group initially assigned in the first treatment course. In addition, totals over all dose cohorts will be given.

“Analysing treatment periods” will be used for reporting of treatment emergent adverse events (AE) and to differentiate between screening, on-treatment, post-treatment and post-study safety data. The inequalities start date \leq onset date of AE $<$ stop date will determine whether the AE will be assigned to the “analysing treatment period” or not. Table 6.1:1 defines the “analysing treatment periods” which will be used for reporting of treatment emergent AEs and safety laboratory parameters.

Table 6.1:1 Definition of analysing treatment periods

| Analysing treatment period | Start date (including) | Stop date (excluding) |
|----------------------------|---|---|
| Screening | Date of informed consent | Date of first administration of trial medication |
| MTD evaluation period | Date of first administration of trial medication | Date of third infusion or (if the third infusion was not administered) Date of first administration of trial medication + 28 days |
| On-treatment | Date of first administration of trial medication | Start date of ‘Follow-up’ |
| Follow-up | Date of end of REP +1 day, i.e. Date of last administration of trial medication + 30 days of REP + 1 day | Start date of ‘Post-study’ |
| Post-study | Last date patient status obtained / last date patient known to be alive + 1 (if patient is lost to follow-up) / date of refusal + 1 day / the date patient died + 1 | DBL + 1 day |

Data recorded between the first administration of trial medication until up to 30 days (Residual effect period; REP) after the last administration of trial medication will be considered as on-treatment.

In addition, to justify the MTD determination, AEs occurring during the MTD evaluation period will be presented separately from those occurring during the complete on-treatment period.

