##### Phase I:

The dose is planned to be escalated in cohorts at pre-defined dose levels based on a maximum escalation of 100%. The provisional dose levels are 20mg, 40mg, 80mg, 160mg, and 320mg. Intermediate or lower dose levels, depending on the number of DLTs observed in the study, may be investigated if agreed upon between Investigator and Sponsor.

For any dose-escalation cohort, at least 3 patients will be required, but two out of those patients must be evaluable patients to escalate dose in next cohort. The DSB will also recommend the size for the next cohort between three to six patients. However, the final decision on the next cohort size will be made by a mutual decision between the TMM and the Coordinating Investigator (CI). After all patients in a cohort have either experienced a DLT or have been observed for at least one cycle (28 days – 2 administrations) without experiencing a DLT, the BLRM will be updated with the newly accumulated data and the overdose risk will be calculated. Based on the model and on additional information (PK, PD patient profiles), the members of the DSB will reach a joint decision on the next dose level to be investigated.

Proprietary confidential information.

© 2019 Boehringer Ingelheim International GmbH or one or more of its affiliated companies. All rights reserved.

This document may not - in full or in part - be passed on, reproduced, published or otherwise used without prior written permission.

During the cohort dose escalation phase, entry into the initial 20mg dose cohort will be allowed after a minimum of 7 days from the first administration of the first patient, and subsequently between patient 2 and 3. If the cohort expands to 6 patients, the 7-day observation period between the subsequent patients must be followed. For subsequent cohorts, enrollment will be allowed after a minimum of 3 days from the first administration of each patient.

Enrollment into the next dose cohort is allowed after the previous dose cohort is found to be safe for all patients in this cohort (e.g. at least 28 days after the first administration of drug in the last patient entered into the cohort). For the purposes of determining dose escalation, Dose Limiting Toxicities will be assessed based on safety data from Cycle 1 (2 administrations – 28 Days), however DLTs will be monitored beyond Cycle 1 and throughout the trial.

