Proprietary confidential information.

In case criterion 1 and 2 are not fulfilled, blood counts and/or the adverse event should be re-evaluated for up to three weeks and documented in the eCRF. In case of a treatment delay, the Sponsor must be notified.

Administration of the trial drug has to be stopped temporarily in case of a DLT (see [Section 5.2.1.1](#)). Patients may continue therapy only after recovery from the DLT to a CTCAE level which allows further therapy based on Investigator assessment and only with a reduced dose of BI 836858. The new dose of BI 836858 must be finally agreed on between the Sponsor and the Investigator. The reduced dose will be valid for all following treatment cycles in the individual patient. A reduction of the dose will be allowed only once for an individual patient during the whole trial. In case a patient experiences a second episode of DLT with the reduced BI 836858 dose, the treatment has to be permanently discontinued. Likewise, treatment has to be discontinued in case the DLT is not reversible. Patients who discontinue treatment will complete an End of Trial Visit and follow-up visits.

Intra-patient dose escalation may be considered after agreement between investigator and sponsor for selected patients. It is restricted to patients who have completed and received a minimum of 8 administrations of BI 836858 and tolerate the treatment well at the time of dose escalation. Intra-patient dose escalation can only be performed at a time when the next higher dose cohort has been reviewed and considered safe by the DSB. The dose escalation step is limited to the dose which has been administered to the next higher cohort. Only one dose escalation will be permitted for a patient. Dose escalations can only occur on Day 1, or Visit 1 of a cycle. After the first dose at the higher dose level, patients have to be monitored for at least 24 hours after the end of the infusion, including a safety laboratory 24 hours after the first administration of the escalated dose of BI 836858. Patients who have escalated to a higher dose and who experience toxicities may be permitted to reduce back to a lower dose, following the criteria described above. A log of all patients pre-screened and enrolled into the study (i.e. having given informed consent) will be maintained in the Investigator Site File (ISF) at the investigational site irrespective of whether they have been treated with investigational drug or not.

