5.1 PRIMARY ENDPOINTS

The primary endpoints in the Phase I part of the trial are the MTD and the number of patients with dose limiting toxicities (DLTs) during the MTD evaluation period.

Maximum tolerated dose (MTD) and number of patients with DLTs during the MTD evaluation period:

The MTD is defined as the highest dose of BI 836858 with less than 25% risk of the true DLT rate being above 33% during the MTD evaluation period. The other primary endpoint, the number of patients with DLTs during the MTD evaluation period will be used to determine the MTD.

MTD evaluation period:

The MTD evaluation period is defined as the time from the first administration of trial medication to start of the third administration of BI 836858, excluding the day of the third administration of BI 836858. In case the third infusion of BI 836858 is not administered, the evaluation period ends 30 days after the last administration.

In case a patient has not completed the required number of administrations due to BI 836858 related toxicity, he/she will not be replaced and this will be considered as DLT. However, patients who have not completed the required number of administrations of BI 836858 for reasons other than BI 836858 related toxicity will be replaced. Patients who were replaced during the MTD evaluation period will not be considered for MTD evaluation. That is, a patient will be considered evaluable for MTD assessment if he/she received at least 2 administrations of BI 836858 or if he/she received less than 2 administrations due to DLT.

The MTD estimate after the dose escalation part of the trial will be obtained on the basis of DLTs observed during the MTD evaluation period. However, for those patients who receive more than one cycle of the treatment, all AEs that constitute a DLT will be considered in the final determination of the dose recommended for the Phase II part.

As part of this additional analysis the probabilities of the Bayesian 2-parameter logistic regression model with overdose control will be also computed including all considered DLTs.

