7.8.1 Adverse events

7.8.1.1 Maximum tolerated dose and dose limiting toxicity

Analysis of MTD will be reported as described in Section 7.4.

In addition, tables displaying DLTs by primary system organ class and preferred term will be provided by initial treatment for the MTD evaluation period for the MTD evaluation set as well as for the treated set over the on-treatment period.

The purpose of these tables is to summarize and document the data that led to the selection of MTD. A summary of the number of patients with DLT within the MTD evaluation period (treatment course 1) and for all treatment courses of the on-treatment period will be given by initial treatment for the treated set.

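### All-course DLTs are tabulated only by starting dose although doses can change, so a DLT after a dose change appears at a dose the patient was no longer receiving

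*SAP*

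**What the plan says.** **Dose can change within a patient.** On escalation, Protocol 4.1.4 says: "It is restricted to patients who have completed and received a minimum of 8 administrations of BI 836858". It adds "The dose escalation step is limited to the dose which has been administered to the next higher cohort" and "Only one dose escalation will be permitted for a patient". On reduction it says "A reduction of the dose will be allowed only once for an individual patient during the whole trial".

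**Late DLTs count.** Protocol 4.1.3 (Phase I) says "DLTs will be monitored beyond Cycle 1 and throughout the trial". SAP 5.1 and 7.4 bring DLTs from later courses into the final RP2D determination. SAP 5.1 adds that the BLRM probabilities "will be also computed including all considered DLTs".

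**Late DLTs are grouped by starting dose.** The general rule in SAP 6.1 is that "patients will be analysed by the treatment group initially assigned in the first treatment course". SAP 7.8.1.1 repeats it for DLTs: the table by system organ class and preferred term is by initial treatment, and the summary "for all treatment courses of the on-treatment period will be given by initial treatment for the treated set".

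**Output by actual dose.** The only one is a listing in SAP 7.8.1.2 that gives the treatment on the day an adverse event started. No table or model uses it. In Protocol 7.3.3 the initial-dose wording belongs to the first-cycle safety analysis; the all-cycle analysis carries no such wording.

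**The concern.** Take a patient who starts at 160 mg, moves to 320 mg after 8 administrations and then has a DLT. The all-course tables show this as a DLT at 160 mg. The 320 mg row shows neither the event nor the patient's exposure. After a dose reduction the misplacement runs the other way: a further DLT at the reduced dose is shown at the higher starting dose.

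The all-course data exist to show toxicity that the Cycle 1 window misses, and the plan uses them for the RP2D. Dose escalation had 21 patients and expansion 6 (protocol synopsis), so one misplaced DLT visibly changes a cohort's rate. The additional BLRM also needs one dose per observation, and SAP 5.1 names none for a patient whose dose changed.

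**Working it through.** **1. Is the MTD analysis affected?** No. The MTD evaluation period ends before the third administration (SAP 5.1), and escalation needs at least 8. A reduction follows a DLT (Protocol 4.1.4), so a patient reduced in Cycle 1 has already been counted with a DLT at the starting dose.

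**2. Model (Protocol 7.1).** logit p(d) = log(α) + β·log(d/160). The prior on (log α, log β) is a three-part normal mixture, with all correlations 0:
- weight 0.90, mean (−2.189, 0.146), SD (2, 1)
- weight 0.05, mean (−0.549, −0.233), SD (2, 1)
- weight 0.05, mean (−4.068, −1.372), SD (5, 0.01)

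With y DLTs in n patients at each dose, the posterior is proportional to prior × Π p(d)^y·(1 − p(d))^(n − y). P(overdose at d) is the posterior probability that p(d) ≥ 0.33, and the limit is 0.25. The posterior was computed by numerical integration on a grid.

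**3. The plan's own figures (Protocol 10.3, Table 10.3: 1).**
- Scenario 8: 0.016 at 160 mg and 0.209 at 320 mg (stated 0.016 and 0.219).
- Scenario 9: 0.702 at 320 mg and 0.052 at 160 mg (stated 0.709 and 0.053).

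All agree within 0.01.

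**4. Assumed data.** The documents give no DLT counts, cohort sizes by dose or number of escalated patients. Assume 0/3 at each of 20, 40 and 80 mg, and 6 starters each at 160 and 320 mg (3 + 3 + 3 + 6 + 6 = 21).

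*Case A.* One DLT in a 320 mg starter, and one in a 160 mg starter after moving to 320 mg. Any further escalated patients have no DLT. Under dose at onset, escalated patients stay in the 160 mg denominator as DLT-free and are added at 320 mg.

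| Assignment | 160 mg | 320 mg | Raw rate at 320 mg | P(overdose at 320 mg) |
|---|---|---|---|---|
| Initial dose | 1/6 | 1/6 | 17% | 0.144 |
| Onset, 1 escalated | 0/6 | 2/7 | 29% | 0.200 |
| Onset, 2 escalated | 0/6 | 2/8 | 25% | 0.146 |
| Onset, 3 escalated | 0/6 | 2/9 | 22% | 0.105 |
| Onset, 4 escalated | 0/6 | 2/10 | 20% | 0.076 |

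If the single escalated patient is instead removed from the 160 mg denominator (0/5), 0.200 becomes 0.209.

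*Case B.* Three 160 mg starters escalate, all three have a late DLT, and there is no Cycle 1 DLT.
- Initial dose (160 mg 3/6, 320 mg 0/6): P(overdose at 320 mg) = 0.202, under the limit.
- Dose at onset (320 mg 3/9): 0.306 with 0/6 kept at 160 mg, or 0.337 with 0/3 there. Both are over the limit.
- P(overdose at 160 mg) moves the other way: 0.025 by initial dose, 0.008 by dose at onset (0/3).

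*Case C.* No late DLT, one DLT in a 320 mg starter, two escalated patients without a DLT. P(overdose at 320 mg) is 0.065 by initial dose (1/6) and 0.030 by dose at onset (1/8).

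**The case against.** **A reader might infer that the rule always understates toxicity at the higher dose.** The documents do not support this. Assigning by dose at onset also moves escalated patients without a DLT to the higher dose, where they enlarge the denominator. In Case A the difference in P(overdose) has gone with two escalated patients and reverses with three. In Case C dose at onset gives the lower value. Dose reductions push in the other direction again. This part of the objection stands.

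**A reader might also infer that the all-DLT BLRM certainly uses initial dose.** SAP 5.1 names no dose, and SAP 6.1 speaks of how data are presented and patients grouped, not of the model. Initial dose is a plausible reading of that silence and no more. For the tables, by contrast, the rule is explicit.

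**Dose at onset is not a clean replacement in the model.** The BLRM describes the probability of a DLT in the first cycle. Escalated patients have had at least 8 administrations and must be tolerating treatment well. Entering them as new patients at the higher dose adds selected tolerators and, if they stay in the lower-dose denominator, counts one person twice as if independent. Grouping by initial dose keeps each patient in one group. This is a trade-off, so replacing one rule by the other in the model is not justified.

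**The practical consequence is limited.** Late DLTs are considered for the RP2D, but the DSB decides it and sees individual patient profiles. The listing of actual treatment at onset lets the dose be recovered by hand. Recruitment stopped during the expansion cohort and Phase II was never started. All this lowers the weight of the point. It does not remove it: the planned tables still show such DLTs at a dose not being given.

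**Conclusion.** The point holds for the tables. SAP 6.1 and 7.8.1.1 place DLTs over the whole on-treatment period at the starting dose while Protocol 4.1.4 lets dose change, and no planned table shows them at the dose received. For the additional BLRM the point is narrower: the dose to enter is not stated.

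The size is uncertain and has no fixed sign. In Case A, P(overdose at 320 mg) moves from 0.144 to between 0.200 and 0.076, depending on how many patients escalate, and no value reaches 0.25. Only the more extreme Case B crosses the limit (0.202 against 0.31 to 0.34). All of this rests on assumed counts. Neither document says how many patients changed dose or had a DLT afterwards; if none did, nothing changes in the DLT counts.

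It would go too far to call the initial-dose tables an error to be removed, or to say that the MTD is at risk. The initial-dose grouping is legitimate as one view, and the MTD endpoint is untouched. What is missing is the second view and a stated rule for the model.

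**What to change.** - **SAP 7.8.1.1:** keep the initial-dose tables. Add one all-course DLT table by dose received at onset, with patients (or infusions) exposed at each dose as the denominator.
- **SAP 5.1:** state which dose the additional all-DLT BLRM uses for patients whose dose changed. Run the other assignment as a sensitivity analysis. Note that escalated patients are selected for tolerating treatment and are not independent new patients, and say whether they stay in the lower-dose denominator.
- **SAP 6.1:** add a cross-reference to this exception. The Cycle 1 MTD analysis stays by initial dose.

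This is a cheap improvement. The treatment on the day of AE onset is already needed for the SAP 7.8.1.2 listing, so the cost is one extra table, one extra model run and a few sentences. The downside is that patients whose dose changed appear under two doses in the new table, which needs a footnote.

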6.2 IMPORTANT PROTOCOL DEVIATIONS

Even though no per protocol population is defined, patients with potentially important protocol deviations (iPD) will be identified and documented.

Potentially important protocol deviations are defined in Table 6.2:1. The final list of iPDs will be confirmed at the last report planning meeting (RPM) before the database lock at the time of the CTR.

If any manual iPDs are identified, they are to be summarized into categories and will be captured in the MQRM/RPM minutes via an accompanying Excel spreadsheet ([3](#)).

Table 6.2:1 Important protocol deviations

| Category/ Code | | Description | Comment/Example | Excluded from |
|-------------------|--|--|--|------------------|
| A | | Inclusion/Exclusion Criteria | | |
| A1 | | Criteria related to safety | | |
| A1.1 ¹ | | Patient has condition that may cause additional risk from study medication | EX 11, IN 4 | None |
| A1.2 ¹ | | Patient has laboratory assessments that may cause additional risk. | EX 6-9 | None |
| A1.3 ¹ | | Patient is unable to comply with the protocol | EX 12, EX 21 | None |
| A1.4 ¹ | | Patient has condition that may interfere with evaluation of safety (and/or efficacy) | EX 3-5, EX 10, EX 13, EX 17-20 | None |
| A2 | | Criteria related to efficacy | | |
| A2.1 ¹ | | Patient does not have trial diagnosis or is not part of the target population | IN 1-3, EX 1, EX 2 (Phase II only) | None |
| B | | Legal criteria | | |
| B1 ¹ | | Informed consent not available/not done | IN 6 | All |
| B2 ¹ | | Informed consent too late | Informed consent date after screening visit date. | None |
| B3 ¹ | | Men or women who are sexually active and not using adequate contraception. | EX 14, EX 15 | None |
| B4 ¹ | | Pregnant or nursing female patient | EX 16, positive pregnancy test | None |
| B5 ¹ | | Patient's age < 18 | IN 5 | None |
| C | | Trial medication and randomization | | |
| C1 ² | | Administration of trial medication not in accordance with the protocol | As marked in the eCRF, after discussion and decision in MQRM | None |
| C2 ² | | Continuation of treatment although criteria for re-treatment are not met | Create listing, decision at MQRM / report planning meetings (RPM), see CTP section 4.1.4 | None |

Table 6.2:1 Important protocol deviations (cont.)

| Category/ Code | Description | Comment/Example | Excluded from |
|-------------------|--|--|------------------|
| C3 ² | (Unjustified) intra-patient dose-escalation | Create listing, decision at MQRM / RPM, see CTP section 4.1.4 | None |
| C4 ² | Withdrawal of patient not performed according to CTP | Create listing, decision at MQRM / RPM, see CTP section 3.3.4 | None |
| C5 ² | Discontinuation of trial drug not performed according to CTP | Create listing, decision at MQRM / RPM, see CTP section 3.3.4 | None |
| C6 ² | Phase II: Wrong stratification factor input during randomization | Create listing comparing IVRS and eCRF information | None |
| D | Restrictions | | |
| D1 ² | Additional experimental anti-cancer, chemo-, immuno-, hormone - or radiotherapy during the treatment period. | Create listing, decision at MQRM / RPM, see CTP section 4.2.2.1 and EX 3, EX 5 | None |
| E | Missing data | | |
| E1 ² | Baseline bone marrow assessment not within the required time-window | Create listing for patients whose bone marrow assessment was not within 14 days prior to first treatment, decision at MQRM / RPM | None |

[1] iPd will be derived automatically

[2] iPd will be identified via individual review at MQRM/RPM/DBL

6.3 PATIENT SETS ANALYSED

The following patient sets are defined for the Phase I part:

- Screened set (SS): This patient set includes all patients who have signed the informed consent. The SS will be used for patient disposition tables.
- Treated set (TS): This patient set includes all patients who were documented to have received at least one dose of trial medication.
- MTD evaluation set: The MTD evaluation set includes all patients from the TS who have not been replaced for the MTD evaluation. Rules for replacement of patients are defined in [Section 5.1](#) and CTP section 3.3.4.1.

The MTD evaluation set will be used for the primary endpoint analyses whereas the TS will be used for all other efficacy and safety analyses in the Phase I part. The list of replaced patients will be provided by the clinical trial monitor no later than at the last RPM and will be attached to the RPM minutes.

No per protocol population will be used for analyses.

6.5 POOLING OF CENTERS

Not applicable because centre/country is not included in the statistical model.

6.6 HANDLING OF MISSING DATA AND OUTLIERS

If not stated otherwise, missing data will not be imputed and will remain missing. Potential outliers will be reported and analysed as observed. Missing or incomplete AE dates will be imputed according to BI standards (4).

For missing laboratory data at Visit 1 (before the very first administration of study medication) data from preceding visits will be used if available.

6.7 BASELINE, TIME WINDOWS, AND CALCULATED VISITS

Study days and visits will be labelled according to the CTP's flow chart.

Unless otherwise specified, baseline is defined as the time-point closest to but prior to the first administration of trial medication in course 1. Note that for some trial procedures (for example body weight, vital signs, laboratory tests) this may be the value measured on the same day the trial medication was started. In these cases it will be assumed that the measurements were taken according to protocol, i.e. prior to first intake of any trial medication.

For laboratory values, baseline is defined as the latest time-point before the very first administration of any trial medication in course 1. When not only the examination date but also time are recorded, the examination time has to be taken into account when defining baseline. That is, a laboratory value on the same date as the first trial drug administration is considered as baseline value if and only if the time of laboratory value is before or the same as the time of first trial drug administration.

